2.3 Amgen Investigational Product Background

Blinatumomab (BLINCYTO[®], AMG 103) is a member of a novel class of bispecific antibody constructs called “bispecific T-cell engagers” or BiTE[®] (Schlereth et al, 2006; Dreier et al, 2003) with dual binding specificities. T cells are bound by its anti-CD3 moiety, whereas B lymphoblasts and cells are bound by the anti-CD19 moiety. This unique feature of blinatumomab allows it to transiently connect malignant cells with T cells, thereby inducing T-cell mediated killing of the bound malignant cell. In preclinical models, blinatumomab-mediated T-cell activation involves the transient release of inflammatory cytokines and proliferation of T cells. The subsequent serial lysis of multiple malignant cells by a single blinatumomab-activated T cell closely resembles a natural cytotoxic T-cell reaction.

Blinatumomab is approved in multiple regions for the treatment of Philadelphia chromosome-negative relapsed or refractory B-cell precursor ALL. Additionally, confirmation of clinical benefit is a condition of approval in multiple countries.

CD19 is highly expressed throughout B-cell development and is present on > 90% of B-cell lineage cancers, including DLBCL. The efficacy of blinatumomab has been evaluated in subjects with B-cell precursor ALL and multiple histologies of NHL, including DLBCL. Refer to Investigators Brochure for efficacy and safety information with the use of blinatumomab as well as for additional information related to the physical, chemical, and pharmaceutical properties and formulation(s).

2.4 Rationale

The current study in high-risk DLBCL subjects who are MRD-positive post-aHSCT will provide an opportunity to further define blinatumomab's safety and efficacy profile. DLBCL tumors are aggressive but potentially curable malignancies in subjects with limited disease, with a 5-year PFS ranging from 80 to 85%. However, there is a subset of subjects with high-risk DLBCL that do substantially worse with only a 25 to 50% PFS at 5 years, and most of these subjects relapse within the first year. In addition, at relapse, high-risk DLBCL subjects historically do very poorly with salvage therapy, including aHSCT. The concept of increasing depth of response by eradication of MRD has been widely established in hematological malignancies. In DLBCL, data on clinical relevance of MRD is evolving. MRD detection via immunoglobulin high-throughput sequencing of CT-DNA was predictive for relapse in 2 retrospective studies. MRD occurred after a median of 3.5 months in one study and was followed by clinical relapse. The other study confirmed the occurrence of MRD followed by clinical relapse. Early detection of disease recurrence via MRD prior to clinical relapse provides the option for early intervention. A potential clinical benefit of intervention in MRD-positive DLBCL, however, has not been investigated yet.

This study focuses on an unmet medical need in subjects with high-risk DLBCL who underwent aHSCT and are currently in CR with detectable MRD in the circulation to improve their PFS by increasing the depth of their responses by eradicating MRD. This study is designed to investigate if preemptive treatment with blinatumomab of subjects that are MRD-positive post-aHSCT will improve subject outcomes and can be administered with a favorable safety profile. In addition, this study may contribute to understanding the relevance of the concept of MRD in order to intervene early when disease is limited and help to improve overall outcomes in DLBCL.

Based on experience with blinatumomab in previous studies, this study will use the stepwise dosing regimen (9/28/112 $\mu\text{g}/\text{day}$) for relapsed/refractory DLBCL. In the previous NHL study, bone marrow clearance was achieved at doses of 15 $\mu\text{g}/\text{m}^2/\text{d}$ (translating into 28 $\mu\text{g}/\text{d}$) while eradication of extramedullary disease needed dose escalation to 60 $\mu\text{g}/\text{m}^2/\text{d}$ (translating into 112 $\mu\text{g}/\text{d}$). Although MRD will be detected in blood, the location of disease is presumed to be in extramedullary sites. MRD assessments at intermediate dose-step and interim timepoints during cycle 1 treatment will be performed to help inform the appropriate choice of dosing regimen in the DLBCL MRD setting.

The single-agent activity of blinatumomab observed in heavily pre-treated subjects coupled with the need for new agents earlier in the course of treatment of high-risk subjects provides a strong rationale for testing blinatumomab in the setting of MRD positivity post aHSCT.

2.5 Clinical Hypotheses

The study will estimate the MRD-negative response rate after treatment with blinatumomab in subjects with high-risk DLBCL who are MRD-positive following aHSCT. The clinical hypothesis is that the MRD-negative response rate will be greater than 10%. Achieving an MRD-negative response rate of 30% would be of scientific and clinical interest.

2.6 Benefit/Risk Assessment

Subjects with high-risk DLBCL represent the greatest challenged population in front-line treatment of DLBCL. Approximately 30% to 50% subjects with high risk will relapse. Autologous hematopoietic stem-cell transplant is recommended in subjects who experience primary induction failure and high-risk first complete remission/first partial remission ([Robinson et al, 2016](#)). In spite of the improved therapies, for a significant portion (approximately 50%) of the subjects who undergo aHSCT, the 3-year progression-free survival remains low at 53% ([Gisselbrecht et al, 2010](#)). The treatment options become very limited after aHSCT. Allogeneic HSCT, a therapy with a high treatment-related mortality rate (up to approximately 25%), is the only curative option for relapse after aHSCT, but the majority of patients are not able to achieve disease control which is a prerequisite for undergoing alloHSCT. There is a significant unmet need for the DLBCL subjects who have undergone aHSCT.

Treating subjects with MRD-positive, high-risk DLBCL post aHSCT presents a potential benefit because these subjects have a high risk of disease relapse. Once relapsed, the

chances of survival are low and the adverse events associated with other treatment options severe.

Known toxicities due to the use of blinatumomab include neurologic events and cytokine release syndrome (CRS), which, in some cases, may be life-threatening. These events may be severe and require temporary interruption or permanent discontinuation of blinatumomab treatment.

Furthermore, there is a risk that the MRD assay could result in a false positive. As such, in this study, this would lead to the administration of 1 cycle of blinatumomab treatment to a patient who is actually MRD-negative, thus exposing a patient to the treatment risks without receiving incremental benefit. Since blinatumomab has not been studied directly in DLBCL subjects who are MRD-negative, this risk is based on available safety data in subjects who achieved complete MRD response (MRD-negative) and continued to receive blinatumomab in Study MT103-203, a phase 2 study evaluating the efficacy and safety of blinatumomab in adult subjects with MRD-positive ALL. The treatment-emergent adverse events from Study MT 103-203 provided information to estimate the potential risk to MRD-negative subjects who may receive blinatumomab treatment due to a false positive MRD result. Of the 64 MRD-negative subjects, 89.1% of subjects experienced at least 1 treatment-emergent adverse event, 29.7% of subjects experienced grade 3 treatment-emergent adverse events, and 18.8% experienced grade 4 treatment-emergent adverse events. There were no grade 5 events among these subjects. The majority of the treatment-emergent adverse events experienced by subjects who received blinatumomab in a second cycle after achieving MRD-negativity in the first cycle of treatment were mild, and none had a fatal outcome.

Experience to-date has shown that adverse events associated with high tumor burden at baseline, such as CRS and neurologic events, appear to become less frequent and severe with reduction of tumor burden. As such, the high unmet medical need in the patient population and the potential for benefit outweighs the risks that may be associated with participating in this study.

3. EXPERIMENTAL PLAN

3.1 Study Design

This is a phase 2, multicenter, open-label, single arm estimation study in adult subjects with high-risk DLBCL that are PET-CT negative post aHSCT. The study will consist of the following periods:

- Screening period (up to **28** days)
- Run-in period of up to 24 months to evaluate MRD status and assess eligibility for treatment assignment
- Treatment period of 12 weeks (which includes 8 weeks of treatment with blinatumomab followed by a 4-week treatment-free period)
- Safety follow-up visit 30 days after the last dose of blinatumomab
- Long-term follow-up period that begins after the safety follow-up visit is completed until 1 year from the first dose of blinatumomab.

The study will enroll approximately 90 subjects with relapsed/refractory, biopsy-proven, high-risk DLBCL who are PET-CT negative at 90 days (\pm 30 days) post aHSCT (see [Section 4.1](#) Part 1 Inclusion and Exclusion criteria). During the run-in period, subjects will be followed by clinic visits at 3, 5, 7, and 9 months, and thereafter every 3 months (\pm 1 week) up to 24 months for monitoring of MRD status in plasma by NGS-based assay. Subjects who remain MRD-negative by the end of the 24-month run-in period will end the study. It is expected that approximately 30 subjects will be MRD-positive either at screening or become MRD-positive during the 24-month run-in period. The number of subjects enrolled may be altered in order to ensure that approximately 30 subjects are assigned to treatment with blinatumomab. Enrollment may be stopped once approximately 30 subjects have been assigned to treatment with blinatumomab.

Subjects who are MRD-positive at enrollment or become MRD-positive during the run-in period, and who meet all other part 2 eligibility criteria (see [Section 4.2](#)), will be assigned to treatment with blinatumomab.

Blinatumomab will be administered as a continuous intravenous (IV) infusion. Cycle 1 will be 12 weeks (84 days) in duration, which includes 8 weeks (56 days) of blinatumomab IV infusion followed by a 4-week (28 day) treatment-free interval. Blinatumomab will be dosed at 9 μ g/day for 7 days, followed by 28 μ g/day for 7 days and 112 μ g/day for 42 days.

MRD status will be assessed at cycle 1 day 1 prior to blinatumomab infusion, on cycle 1 days 15 and 43, the end of the blinatumomab infusion (day 57), and 2 weeks after the end of the blinatumomab infusion (day 71 + 3 days) to evaluate disease status. A PET-CT will be performed only if a subject remains MRD-positive (day 57 of cycle 1 assessment) after blinatumomab or has clinical signs and symptoms of disease progression.

A safety follow-up visit will occur 30 days (+ 3 days) after the last dose of blinatumomab for assessment of disease-related events, adverse events, and serious adverse events. A long-term follow-up period to assess disease status and OS begins at completion of the safety follow-up visit and continues for 1 year from the first dose of blinatumomab. Subjects will be followed via clinic visit every 3 months (\pm 2 weeks) for MRD assessment and by institutional standard of care disease evaluation (PET-CT or CT) until relapse at which time the subject will be followed for survival via telephone contact.

A Data Review Team (DRT) will monitor the study for safety on a regular basis (see [Section 10.3.1](#)).

The overall study design is described by a [study schema](#) at the end of the protocol synopsis section.

The study endpoints are defined in [Section 10.1.1](#).

3.2 Number of Sites

Approximately 35 sites in North America, Australia, and Europe will participate in the study. During the conduct of the study, additional countries, regions or sites may be added if necessary. Sites that do not enroll subjects within 6 months of site initiation may be closed.

3.3 Number of Subjects

Participants in this clinical investigation shall be referred to as “subjects”.

Approximately 90 subjects will be enrolled in the study. It is expected that approximately 30 subjects will be MRD-positive at screening or become MRD-positive during the 24-month run-in period. The number of subjects enrolled may be altered in order to ensure that approximately 30 subjects are assigned to treatment with blinatumomab. Enrollment may be stopped once approximately 30 subjects have been assigned to treatment with blinatumomab.

For sample size considerations see [Section 10.2](#).

3.4 Replacement of Subjects

Subjects who are withdrawn or removed from treatment or the study will not be replaced.

3.5 Estimated Study Duration

3.5.1 Study Duration for Subjects

The total study duration for an individual subject will vary from approximately 1 to 3 years. This includes a **28**-day screening period, a run-in period of up to 24-months, a 12-week treatment period (8 weeks of treatment with blinatumomab followed by a 4-week treatment free period), a 30-day safety follow-up and a long term follow-up period that begins after the safety follow-up period until 1-year from the first dose of blinatumomab.

3.5.2 End of Study

Primary Completion: The primary completion date is defined as the date when the last subject is assessed or receives an intervention for the final collection of data for the primary endpoint, for the purposes of conducting the primary analysis, whether the study concluded as planned in the protocol or was terminated early.

The primary completion date is the date when data for the primary endpoint are last collected for the purposes of conducting the primary analysis.

If the study concludes prior to the primary completion date originally planned in the protocol (ie, early termination of the study), then the primary completion will be the date when the last subject is assessed or receives an intervention for evaluation in the study (ie, last subject last visit).

End of Study: The end of study date is defined as the date when the last subject is assessed or receives an intervention for evaluation in the study (ie, last subject last visit), following any additional parts in the study (ie, long-term follow-up), as applicable.

4. SUBJECT ELIGIBILITY

Investigators will be expected to maintain a screening log of all potential study candidates that includes limited information about the potential candidate (eg, date of screening).

Part 1 eligibility criteria will be evaluated during screening to establish enrollment in the study. Part 2 eligibility criteria will be evaluated in order to assign subjects to treatment with blinatumomab. Part 2 eligibility will be assessed at any time after enrollment and through the run-in period at the time when MRD status becomes positive (see [Section 5](#)).

Before any study-specific activities/procedure, the appropriate written informed consent must be obtained (see [Section 11.1](#)).

4.1 Inclusion and Exclusion Criteria – Part 1

4.1.1 Inclusion Criteria – Part 1

- 101 Subject has provided informed consent prior to initiation of any study-specific activities/procedures or subject's legally acceptable representative has provided informed consent prior to any study-specific activities/procedures being initiated when the subject has any kind of condition that, in the opinion of the investigator, may compromise the ability of the subject to give written informed consent.
- 102 Age \geq 18 at time of informed consent
- 103 Biopsy-proven DLBCL excluding DLBCL that represents transformation of indolent NHL

Note: Lymphoblastic Lymphoma and Burkitt Lymphoma histology are not eligible

- 104 Subject has \geq 1 characteristic feature of high-risk DLBCL:
- High-risk first complete remission (defined as interim PET-CT positive or $<$ complete remission to frontline chemotherapy AND achieved complete remission to platinum-containing salvage)
 - Relapse within 1 year of diagnosis
 - Secondary aalPI $>$ 1 (see [Appendix D](#))
 - Partial response/partial metabolic response after minimum of 2 cycles of platinum-containing salvage chemotherapy
 - C-myc rearrangement
- 105 aHSCT with high-dose chemotherapy following first (or later) salvage treatment.
- 106 PET-CT negative (Deauville score \leq 3) 90 days (\pm 30 days) post aHSCT
- 107 Available relapsed and/or diagnostic pathology formalin-fixed paraffin-embedded (FFPE) tumor block or slide samples at the time of enrollment including the successful identification of malignant clone sequences by the central laboratory.
- 108 MRD plasma sample collected \leq 3 weeks **after the** post aHSCT PET-CT scan
- 109 Eastern Cooperative Oncology Group (ECOG) performance status \leq 2.
- 110 Adequate organ function determined \leq 3 weeks prior to enrollment defined as follows:

Hematological:

- Absolute neutrophil count (ANC) \geq $1.0 \times 10^9/L$
- Platelet count \geq $75 \times 10^9/L$
- Hemoglobin \geq 8 g/dL

Renal:

- Creatinine clearance \geq 50 mL/min Cockcroft-Gault equation

Hepatic:

- Aspartate aminotransferase (AST) and alanine aminotransferase (ALT) < 3 x upper limit of normal (ULN)
- Total bilirubin < 2 x ULN (unless Gilbert's Disease or if liver involvement with lymphoma)

111 Subject will be available to complete all protocol-required study visits or procedures, and/or to comply with all required study procedures to the best of the subject's and investigator's knowledge including but not limited to:

- Completion of up to a 24-month run-in period
- Completion of all regularly scheduled study visits including blood draws for MRD assessment, clinical disease state assessment, PET-CT scans (ie, at time of MRD positivity or relapse), assignment to treatment with blinatumomab

4.1.2 Exclusion Criteria – Part 1

- 201 Clinically relevant CNS pathology such as epilepsy, seizure, paresis, aphasia, stroke, severe brain injury, dementia, Parkinson's disease, cerebellar disease, organic brain syndrome, and psychosis
- 202 Evidence of CNS involvement with DLBCL **at disease evaluation obtained prior to starting blinatumomab**
- 203 Current autoimmune disease or history of autoimmune disease with potential of CNS involvement
- 204 Prior anti-CD19 directed therapies
- 205 Prior alloHSCT
- 206 Received radiation \leq 2 weeks prior to enrollment
- 207 Infection with human immunodeficiency virus or chronic infection with hepatitis B virus (hepatitis B surface antigen positive) or hepatitis C virus (anti-hepatitis C virus positive)
- 208 History of malignancy other than DLBCL within the past 3 years with the following exceptions:
- Malignancy treated with curative intent and with no known active disease present for \geq 3 years before enrollment and felt to be at low risk for recurrence by the treating physician
 - Adequately treated non-melanoma skin cancer or lentigo maligna without evidence of disease
 - Adequately treated cervical carcinoma in situ without evidence of disease

- Adequately treated breast ductal carcinoma in situ without evidence of disease
 - Prostatic intraepithelial neoplasia without evidence of prostate cancer
 - Adequately treated urothelial papillary noninvasive carcinoma or carcinoma in situ
- 209 Subject has known hypersensitivity to immunoglobulins or any of the products or components to be administered during dosing.
- 210 History or evidence of any other clinically significant disorder, condition or disease (with the exception of those outlined above) that, in the opinion of the investigator or Amgen physician, if consulted, would pose a risk to subject safety or interfere with the study evaluation, procedures or completion.
- 211 Women who are pregnant or breastfeeding or planning to become pregnant or breastfeed while receiving blinatumomab and for an additional 48 hours after the last treatment dose of blinatumomab. (Females of child bearing potential should only be included after a negative highly sensitive urine or serum pregnancy test.)
- 212 Women of childbearing potential unwilling to use an acceptable method of effective contraception while receiving blinatumomab and for an additional 48 hours after last dose of blinatumomab.

Note: The pregnancy, breastfeeding and contraceptive requirements are specific to blinatumomab. The investigator is responsible for providing the subject (male and female) with pregnancy and breastfeeding (female only) avoidance requirements for other medications given during the study.

- 213 Currently receiving treatment in another investigational device or drug study or less than 30 days since ending treatment on another investigational device or drug study. Other investigational procedures while participating in this study are excluded.

4.2 Inclusion and Exclusion Criteria – Part 2

4.2.1 Inclusion Criteria – Part 2

- 112 MRD-positive assessment (by NGS analysis) at enrollment or at any time during the run-in 1 period
- 113 PET-CT negative (defined by Deauville criteria ≤ 3) at run-in 2 performed ≤ 3 weeks from **MRD test result available to the site at run-in 1**. Historical PET-CT are allowed if performed ≤ 6 weeks from day 1 (first dose of blinatumomab) and subject has no clinical signs or symptoms suggestive of disease progression (eg, increase in lactate dehydrogenase [LDH] not otherwise explained)

114 Adequate organ function determined ≤ 7 days prior to treatment assignment with blinatumomab as follows:

Hematological:

- ANC $\geq 1.0 \times 10^9/L$
- Hemoglobin ≥ 8 g/L
- Platelet count $\geq 75 \times 10^9/L$

Renal:

- Creatinine clearance ≥ 50 mL/min Cockcroft-Gault equation

Hepatic:

- AST and ALT $< 3 \times$ ULN
- Total bilirubin $< 2 \times$ ULN (unless Gilbert's Disease or if liver involvement with lymphoma)

4.2.2 Exclusion Criteria – Part 2

214 Subject has active infection requiring systemic therapy

215 Any change in the part 1 eligibility criteria during the run-in period.

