5. SUBJECT ENROLLMENT

Before subjects begin participation in any study-specific activities/procedures, Amgen requires a copy of the site's written institutional review board/independent ethics committee (IRB/IEC) approval of the protocol, informed consent form, and all other subject information and/or recruitment material, if applicable (see [Section 11.2](#)).

All subjects or legally acceptable representatives must personally sign and date the Amgen approved informed consent form before commencement of study-specific activities/procedures.

A subject is considered enrolled when the investigator decides that the subject has met all Part 1 eligibility criteria. The investigator is to document this decision and date, in the subject's medical record and in/on the enrollment case report form (CRF).

Each subject who enters into the screening period for the study (defined as the point at which the subject or subject's legally acceptable representative signs the informed consent form) receives a unique subject identification number before any study-related activities/procedures are performed. This number will be used to identify the subject throughout the clinical study and must be used on all study documentation related to that subject. The subject identification number must remain constant throughout the entire

clinical study; it must not be changed after initial assignment, including if a subject is rescreened.

Subjects not meeting Part 1 eligibility criteria are permitted to rescreen 1 additional time after failing the first screening.

Part 2 eligibility criteria will be evaluated at any time after enrollment through the 24-month run-in period at the time when MRD status becomes positive (see [Section 4.2](#)). Subjects who do not meet Part 2 eligibility criteria will end the study.

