Appendix A. Reference Values/Toxicity Grades

Safety Laboratory Data

Treatment emergent laboratory abnormalities are defined as those which occur between the start of the first infusion of blinatumomab and the end of the treatment period.

Safety laboratory values below a distinct limit (eg, detection limit, documented as “< [limit]”) will be substituted by half of the limit and values above a distinct limit (documented as “> [limit]”) will be substituted by the limit itself for all analyses.

Grading (based on CTCAE version 4.03 or above) will be assigned to each laboratory result as detailed in [Table 14-1](#). Depending on the toxicity definition, the same result may be assigned to two gradings for deviations towards higher or lower values. In case no lower limit of normal is provided for the absolute lymphocyte, neutrophils or leukocyte counts, it will not be differentiated between grade 1 and grade 0 results for these parameters. Values not meeting any of the criteria will be assigned a grade 0.

Table 14-1. Grading of Selected Laboratory Parameters

Laboratory Parameter [Unit]	Grade 1	Grade 2	Grade 3	Grade 4
Lymphocytes [G/L]	0.8 - < LLN	0.5 - < 0.8	0.2 - < 0.5	< 0.2
Neutrophils [G/L]	1.5 - < LLN	1.0 - < 1.5	0.5 - < 1.0	< 0.5
Leukocytes [G/L]	3.0 - < LLN	2.0 - < 3.0	1.0 - < 2.0	< 1.0
Platelets [G/L]	75 - < LLN	50 - < 75	25 - < 50	< 25
Hemoglobin [g/L]*	100 - < LLN	80 - < 100	65 - < 80	< 65
Albumin [g/L]	30 - < LLN	20 - < 30	< 20	not defined
AST*	> ULN – 3*ULN	> 3*ULN – 5*ULN	> 5*ULN – 20*ULN	> 20*ULN
ALT *	> ULN – 3*ULN	> 3*ULN – 5*ULN	> 5*ULN – 20*ULN	> 20*ULN
GGT	> ULN – 2.5*ULN	>2.5*ULN – 5*ULN	> 5*ULN – 20*ULN	> 20*ULN
Bilirubin	> ULN – 1.5*ULN	>1.5*ULN – 3*ULN	> 3*ULN – 10*ULN	> 10*ULN
Fibrinogen^	%change of BL <25% or 0.75*LLN - < LLN	25%- <50% of BL or < 75*LLN – 0.5*LLN	50% - <75% of BL or < 0.5* LLN – 0.25*LLN	>= 75% of BL or < 50mg/dL or < 0.25*LLN

Page 1 of 2

Footnotes defined on the next page of the table

Table 14-1. Grading of Selected Laboratory Parameters

Laboratory Parameter [Unit]	Grade 1	Grade 2	Grade 3	Grade 4
Corrected Calcium [mmol/L]*	2.0 - < LLN	1.75 - < 2.0	1.5 - < 1.75	< 1.5
Potassium [mmol/L]*	not defined	3.0 - < LLN	2.5 - < 3.0	< 2.5
Lipase	> ULN – 1.5*ULN	> 1.5*ULN – 2.0*ULN	> 2.0*ULN – 5.0*ULN	> 5.0*ULN
Amylase	> ULN – 1.5*ULN	> 1.5*ULN – 2.0*ULN	> 2.0*ULN – 5.0*ULN	> 5.0*ULN

Page 2 of 2

BL: baseline value, LLN: Lower limit of normal, ULN: Upper limit of normal

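### The Part 2 hemoglobin limit (criterion 114) is printed as 8 g/L and the Part 1 limit (criterion 110) as 8 g/dL, a tenfold difference that nothing in the protocol explains

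*Protocol*

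**What the plan says.** Eligibility is assessed twice. Part 1 criteria decide enrollment. Part 2 criteria decide assignment to blinatumomab and are applied when a subject is MRD-positive, at enrollment or during a run-in of up to 24 months.

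- Protocol 4.1.1, criterion 110 (Part 1, within 3 weeks before enrollment): "Hemoglobin \geq 8 g/dL".
- Protocol 4.2.1, criterion 114 (Part 2) opens with "Adequate organ function determined ≤ 7 days prior to treatment assignment with blinatumomab as follows" and lists "Hemoglobin ≥ 8 g/L".
- Protocol 4.2.2, exclusion 215 (Part 2) adds: "Any change in the part 1 eligibility criteria during the run-in period".
- Protocol 5 gives the consequence of failing: "Subjects who do not meet Part 2 eligibility criteria will end the study".
- SAP Appendix A, Table 14-1 grades hemoglobin in g/L, in the row that begins "Hemoglobin [g/L". Grade 2 is 80 to below 100, grade 3 is 65 to below 80, and grade 4 is below 65.

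**The concern.** Criteria 110 and 114 are parallel lists, yet one limit differs by a factor of ten through its unit. Criterion 114 is the check nearest to first dosing. The criterion 110 value can be about two years old for a subject who turns MRD-positive late in the run-in.

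At stake is a single, unambiguous eligibility decision before each first dose. A subject who satisfies the hemoglobin line of criterion 114 as printed may be well below the limit in criterion 110. Whether that subject is treated or leaves the study then depends on how the site reads exclusion 215. Deviation reporting inherits the ambiguity, because SAP Section 9.3 looks to the protocol for what counts as an eligibility deviation.

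**Working it through.** The plan derives no figure here that could be reproduced. The check is a comparison of the two lists and a unit conversion.

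**Step 1. The two organ-function lists side by side (Protocol 4.1.1 and 4.2.1).**

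| Parameter | Criterion 110 (Part 1) | Criterion 114 (Part 2) | Same? |
|---|---|---|---|
| Neutrophils | at least 1.0 × 10⁹/L | at least 1.0 × 10⁹/L | yes |
| Platelets | at least 75 × 10⁹/L | at least 75 × 10⁹/L | yes |
| Hemoglobin | at least 8 g/dL | at least 8 g/L | **no** |
| Creatinine clearance | at least 50 mL/min | at least 50 mL/min | yes |
| AST and ALT | below 3 × ULN | below 3 × ULN | yes |
| Total bilirubin | below 2 × ULN | below 2 × ULN | yes |

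Hemoglobin is the only limit that differs.

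**Step 2. Conversion (1 g/dL = 10 g/L).**

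- Criterion 110: 8 × 10 = 80 g/L.
- Criterion 114: 8 g/L, or 8 / 10 = 0.8 g/dL.
- Ratio: 80 / 8 = 10.

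**Step 3. Comparison with the SAP's grading scale.**

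- 8 / 65 = 0.123, so the printed Part 2 limit is about 12% of the grade 4 cut.
- 65 / 8 = 8.1, so the grade 4 cut is about eight times the printed limit.
- A subject at 60 g/L, grade 4 on Table 14-1, would satisfy the hemoglobin line of criterion 114 (60 is above 8).

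**Step 4. An illustrative subject at the treatment assignment visit with hemoglobin 75 g/L (grade 3).**

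- Criterion 114: 75 is above 8, so the hemoglobin line is met.
- Criterion 110, if applied again: 75 is below 80, so it is not met.
- Exclusion 215: if a change means no longer meeting a Part 1 limit, the subject is excluded and ends the study. If 215 is not read as re-applying laboratory limits that criterion 114 already covers, hemoglobin does not stop treatment.

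**Step 5. Is this superseded text?** No. The line stands in the operative criterion. The Amendment 3 change list touches only the time window of criterion 114 (from 2 weeks to 7 days) and records no change to hemoglobin.

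**The case against.** The strongest reply is that Part 2 requirements are cumulative. A subject must meet criterion 114 and must also not trigger 215. On its natural reading, 215 excludes anyone who has ceased to meet a Part 1 criterion, hemoglobin included. Table 4 schedules hematology at run-in 2, the treatment assignment visit, and Table 5 lists hemoglobin, so a current value is at hand. Criterion 210, also a Part 1 criterion, lets the investigator exclude a clinically significant condition that poses a safety risk.

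This stands in large part. A reader might infer from criterion 114 that the pre-treatment check for anemia is inoperative, or that Part 2 excludes nobody for low hemoglobin. The documents do not support that: it holds for one line of one criterion read alone, not for Part 2 as a whole. What 215 does not do is remove the inconsistency. It leaves change undefined, does not say that criterion 110 values are applied again, and does not say which limit governs. The window in criterion 110 is also tied to enrollment, not to treatment assignment.

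A second reply is that the matching lists make a unit slip obvious, so no site would apply 0.8 g/dL. That is plausible, and nothing in the documents suggests that a site would. It is still an inference: the protocol does not say that the line is an error, and an eligibility limit should not depend on readers correcting it.

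Third, the point turns on one letter printed in one place, since Amendment 3 reprints only the opening sentence of criterion 114. That is a reason to look at the protocol page. No evidence suggests that the letter was lost in copying.

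Finally, a reader might assume that the eligibility case report form checks carry the same value. The documents do not describe such a check. SAP 8.1 refers only to a separate data validation plan.

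**Conclusion.** The inconsistency is real and lies in the current text. The hemoglobin limits in criteria 110 and 114 differ exactly tenfold, all other organ-function limits agree, and no explanation is given. Taken literally, the hemoglobin line of criterion 114 screens out practically no one. This rests on its position relative to the SAP grade 4 cut, because the documents give no hemoglobin distribution for these subjects. Exclusion 215 limits the consequence without settling it.

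The pattern looks like a unit slip, but the documents do not establish that, and this review takes no position on which limit is right. The effect is confined to who may be assigned to treatment and how eligibility deviations are classified. The sample size of 30, the confidence interval table and the DLT stopping boundary do not depend on this limit.

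**What to change.** Reconcile criteria 110 and 114 so that the hemoglobin limit and its unit are consistent. If a difference between Part 1 and Part 2 is intended, state it and give the reason. In the same change, make clear how exclusion 215 relates to the two criteria: whether Part 1 laboratory limits are applied again at run-in 2, and which criterion governs if they disagree. The choice of limit belongs to the sponsor.

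The cost is one unit and one clarifying sentence in an amendment or clarification memo. No analysis, table or sample size has to be redone.
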